4.2 Avoiding Bias

4.2.1 Patient enrollment

All infants with BPBP between 0 and 12 weeks of age who present for treatment to a participating site will be offered participation in this study.

4.2.2 Surgeon blinded to SRS score

Surgeons will be blinded to neuroradiologist-derived SRS score. SRS score will not be put into the medical record so that the surgeons are blinded to the SRS score.

4.2.3 Standardization of indications for surgery

Surgeons will adhere to standard indications for microsurgery in infants with BPBP. These are: 1) flail arm and Horner's syndrome 2) Toronto score less than 3.5, 3) failure to recover antigravity elbow flexion and/or antigravity shoulder abduction (AMS score for elbow flexion and/or abduction less than 5), 4) failure to bring the hand to the mouth (cookie test), or other clinical indication of lack of appropriate nerve recovery.

4.3 Study Procedures

4.3.1 Study Visits

At the baseline visit, we will collect patient demographics, prenatal and perinatal history, as well as information on any concomitant birth injuries. A standardized physical examination will be conducted at the enrollment visit and all subsequent study visits, consisting of the Toronto Score and AMS score. The Narakas score and the MRI will take place at or around the time of enrollment into the study. At the time of the MRI scan, the neuroradiologist will document the status of each nerve root as normal, post-ganglionic rupture, or pre-ganglionic avulsion, in addition to calculating the numerical SRS. For those infants who undergo microsurgery, we will document the indications for surgery, operative findings at each nerve root, and procedure performed at each nerve root.

[figure not shown]
4.3.2 MRI Scan and Shriners Radiological Score

An MRI will be performed according to the protocol specified in Appendix A. Families will be given instructions prior to their MRI appointment to keep their child awake prior to the exam and to feed them within 30 minutes of the exam to increase the chance of the baby being sleepy during the exam time. Tips for a successful MRI and website links to the MRI sounds and a MRI cartoon may also be provided. Each infant will be positioned in an MRI scanner either using a swaddle blanket or using a vacuum suction controlled infant positioner, the MedVac Immobilizer (CFI Medical, Fenton, MI) [26]. The MRI scanning protocol is composed of a localizer sequence followed by traditional sagittal T2 sequence and 3D proton density CUBE (General Electric trade name, Milwaukee, WI) or SPACE (Siemens Medical USA, Malvern, PA) coronal sequence oriented in the plane of the cervical spine and extended anteriorly to include the involved brachial plexus. The total scanning will be approximately 8 minutes excluding initial positioning time, of which the localizer, traditional sagittal T2 and coronal 3D proton density CUBE/SPACE sequences are 1 minute, 3.4 minutes and 3.5 minutes respectively. Subjects' experience with the MRI scanning process will be

recorded, e.g. the number of times the subject wakes up during the scan or the total time needed to obtain the scan.

Each subject's MRI scan will be reviewed independently by neuroradiologist investigators. The neuroradiologists will interpret the MRI scan and report their findings in the medical record as per standard clinical protocols. Surgeons and families will be aware of these findings and will be able to view the images. However, the SRS calculation will be performed outside the medical record and will not be available to surgeons until after data collection is completed in order to minimize bias. Our pilot data demonstrated inter-rater reliability (Krippendorff's alpha) of 0.78 for calculation of the SRS. The neuroradiologist investigators at the other study centers will read and calculate SRS scores for the pilot study subjects with the goal of exceeding an inter-rater reliability of 0.75 with the other neuroradiologists prior to testing study subjects. In addition, during the study period, a subset of MRI scans will be de-identified and shared between institutions for the purposes of inter-observer and intra-observer analysis. Figure 1 illustrates the calculation of the SRS score from the MRI findings. Each injured level is first assigned 1 point, with additional points assigned for pre-ganglionic injuries: 2 points for each absent nerve rootlet, 2 points for each pseudomeningocele, 0.5 points for each abnormal nerve rootlet; and for post-ganglionic injuries: 1.5 points for each neuroma and 0.5 points for each abnormal nerve. If the zone of injury includes both the pre- and post-ganglionic regions, only the pre-ganglionic injury is scored. The total radiologic score ranges from 0 points (no evidence of nerve root injury on MRI) to 25 points (all 5 levels with pre-ganglionic pseudomeningoceles and absent nerve rootlets). In addition, the neuroradiologist will score each nerve root level as intact, post-ganglionic rupture, or pre-ganglionic avulsion. This information will then be compared with the findings at surgery as described above for those infants who undergo surgery.

Figure 1. Calculation of the Shriners Radiological Score (SRS)

4.3.2.1 Subjects who do not complete the scan or end up with unusable images can repeat the MRI up to two additional times as long as they are within the eligibility window.

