4.3.6 Description of study treatments or exposures/predictors

The primary predictor is the MRI-based Shriners Radiological Score (SRS.) Each patient's MRI will be read by the local study neuroradiologist and given a score between 0 and 25. The secondary predictors are the specific neuroradiologist interpretations of the MRI at each level (for later comparison with intraoperative findings).

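### The plan blinds the surgeon to the SRS but not the SRS reader to the infant's clinical findings, so upward bias in the AUC cannot be excluded

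*Combined protocol and SAP*

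**What the plan says.** **Who scores, and when.** Section 4.3.6 names the primary predictor and its reader: "Each patient's MRI will be read by the local study neuroradiologist and given a score between 0 and 25". Section 4.3.1 places the scoring at the time of the scan, where the neuroradiologist records the status of each root "in addition to calculating the numerical SRS".

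**The clinical report.** Section 4.3.2 gives the neuroradiologist investigators the clinical report as well: "The neuroradiologists will interpret the MRI scan and report their findings in the medical record as per standard clinical protocols".

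**Blinding that is specified.** Section 4.2 (Avoiding Bias) has three items: offering enrollment to all presenting infants, surgeon blinding, and standard surgical indications. The blinding item is: "Surgeons will be blinded to neuroradiologist-derived SRS score". Section 4.3.2 supports it by stating that "the SRS calculation will be performed outside the medical record".

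**Independent and de-identified reads.** Section 4.3.2 also says: "Each subject's MRI scan will be reviewed independently by neuroradiologist investigators". It does not say what the reads are independent of. De-identification appears twice. In section 4.3.2, "a subset of MRI scans will be de-identified and shared between institutions for the purposes of inter-observer and intra-observer analysis". In section 7.2.1, the first two scans at each site are de-identified and read by all three neuroradiologists. Neither section says that these reads supply the score for the primary analysis.

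**The concern.** The safeguards all run one way, from the score to the surgeon. Nothing covers the other direction, from the examination to the score. If a reader knows that an arm looks severely affected, borderline images may be scored higher. If early severity is also related to the later decision for surgery, the predictor then carries some clinical information, and the AUC no longer measures what the images alone show.

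Three results are exposed:

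- the primary AUC, set in section 8.3 against a null of 0.75 and a target of 0.90;
- the possible comparison in section 8.4 of the SRS with the AMS as an earlier detection method, because a score read with the AMS in view is not separate from its comparator;
- the root-level weighted kappa, because root status is recorded at the same read.

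**Working it through.** **1. Is there a safeguard elsewhere?**

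| Safeguard | Section | Does it keep the examination from the SRS reader? |
|---|---|---|
| Surgeon blinded to the SRS | 4.2.2 | No; it protects the decision |
| SRS kept outside the medical record | 4.3.2 | No; same direction |
| Scans reviewed independently | 4.3.2 | Undefined; may mean only independent of other readers |
| De-identified subset | 4.3.2 | Reliability only; number not stated |
| First two scans per site | 7.2.1 | Quality control only; 2 × 3 sites = 6 scans |

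No section withholds the AMS, Toronto score, Narakas score or clinic notes from the reader.

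**2. Is examination information available at the read?** Section 4.3.1 has Toronto and AMS done at enrollment, with the Narakas score and the MRI at or around enrollment. Section 4.4.2.2 plans a same-day clinic visit and MRI for infants first seen between 28 days and 4 months. Section 4.2.3 lists flail arm with Horner's syndrome, the Toronto score and AMS items among the indications for surgery.

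**3. Is there room for judgment in the score?** Some. Under section 4.3.2 an injured level earns 1 point, and an abnormal rootlet or abnormal nerve earns 0.5. Pilot inter-rater alpha was 0.78.

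**4. The plan's own figure.** Section 8.3 gives N = 70 for AUC 0.90 against 0.75, with a 30% surgical rate, 80% power and 5% type I error (sidedness not stated). I used a one-sample test with Hanley-McNeil variance, where n1 and n0 are the surgical and non-surgical numbers:

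Var(A) = [A(1−A) + (n1−1)(A/(2−A) − A²) + (n0−1)(2A²/(1+A) − A²)] / (n1·n0)

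With n1 = 21 and n0 = 49, SE(0.75) = 0.0683 and SE(0.90) = 0.0473. One-sided power = Φ[(0.90 − 0.75 − 1.645 × 0.0683)/0.0473] = 0.79, and the N for 80% power is 72. The plan's 70 is therefore approximately reproduced as a one-sided test. Blinding the reader does not change N.

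**5. Size of a possible bias: illustration only.** The documents give none of these inputs. Assume a binormal score with true AUC A. The reader adds s within-group SDs when the examination looks severe, and that impression has sensitivity Se and specificity Sp for later surgery. With z = Φ⁻¹(A) and d = s/√2:

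Observed AUC = [Se(1−Sp) + (1−Se)Sp]·A + Se·Sp·Φ(z+d) + (1−Se)(1−Sp)·Φ(z−d)

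Worked case: A = 0.75, s = 0.5, Se/Sp = 0.8/0.7. Then Φ(z+d) = 0.848 and Φ(z−d) = 0.626, so the observed AUC = 0.38 × 0.75 + 0.56 × 0.848 + 0.06 × 0.626 = 0.797.

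| Shift s | Se/Sp | True 0.75 reads | True 0.80 reads | True 0.85 reads |
|---|---|---|---|---|
| 0.2 | 0.6/0.6 | 0.758 | 0.807 | 0.855 |
| 0.5 | 0.6/0.6 | 0.765 | 0.812 | 0.859 |
| 0.25 | 0.8/0.7 | 0.776 | 0.822 | 0.868 |
| 0.25 | 0.9/0.8 | 0.787 | 0.832 | 0.876 |
| 0.5 | 0.8/0.7 | 0.797 | 0.840 | 0.882 |
| 0.5 | 0.9/0.8 | 0.818 | 0.858 | 0.897 |

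An uninformative examination (0.5/0.5) gives no inflation: 0.75 reads 0.749 at s = 0.2 and 0.744 at s = 0.5, slightly lower because an unrelated shift only adds noise.

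**6. Consequence for the test.** Under the one-sided test of step 4 with 21/49, if the unbiased AUC is 0.75, an assumed bias of 0.02 raises the chance of rejecting 0.75 from 5% to 8%, and a bias of 0.05 raises it to 16%.

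**The case against.** The strongest case against has four parts.

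- **The documents do not say what the reader sees.** A reader might infer that the examination is in front of the neuroradiologist and that the AUC is therefore biased upward. The text does not support that. The phrase about standard clinical protocols governs the clinical report, and the SRS is calculated separately. This stands: what is established is an unspecified safeguard, not a demonstrated bias.
- **The read comes before the decision.** A reader might also infer that the score absorbs the very findings that decide surgery. Scans fall between 28 days and 4 months of age, with lead-PI approval needed after 90 days (3.2.2). The decision is typically made by 6 months (8.1), after serial examination, and several of the listed indications concern failure to recover. This stands too. The possible overlap is with early findings, such as flail arm with Horner's syndrome or early AMS and Toronto scores, and is likelier for later scans.
- **Section 1.1 says that degrees of injury cannot be told apart on the initial examination.** This argues for the lower end of the illustration, and no passage supports 80-90% sensitivity. It does not dispose of the point, because the statement concerns the initial examination and scans are allowed up to 4 months.
- **The score counts defined findings, and readers are calibrated.** Absent rootlets, pseudomeningoceles and neuromas carry most of the points, and readers train on the pilot scans. This limits the room for a shift but does not replace blinding.

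**Conclusion.** The gap is real: no section blinds the SRS reader to clinical findings, and the planned de-identified reads do not fill it. Upward bias in the AUC, and in any comparison with the AMS, cannot be excluded. Whether it occurs, and how large it would be, cannot be determined from the documents.

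On the assumptions shown, a true AUC of 0.75 could read anywhere from 0.75 with no inflation, through about 0.76-0.77 under weak leakage, to about 0.80-0.82 under strong leakage. The top of that range should not be quoted alone. The whole range rests on assumed shifts and an assumed accuracy of the early examination.

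This is a worthwhile, low-cost improvement to the design, not an error that invalidates it. It is also distinct from another link between predictor and endpoint: surgeons see the images and the report and may use them in deciding (4.3.2, 8.1). Blinding the reader leaves that link in place.

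**What to change.** Add an item to section 4.2: the SRS and root status used in the primary and secondary analyses are scored on de-identified images, with only age and affected side known. They are locked before the reader opens the referral or examination record and before the clinical report is written. Align sections 4.3.1, 4.3.2 and 4.3.6 with this, say in 4.3.2 what the reads are independent of, and state in 8.4 that the locked score is the one analyzed. Scans already scored without this safeguard would need a fresh de-identified read.

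The cross-site de-identified reads already planned can be used to compare local with off-site scores, but only descriptively: the quality-control set is six scans and the size of the reliability subset is not stated.

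For new scans the cost is a changed reading order and a small workflow burden for the local reader. No extra reader or patients are needed, and N is unchanged.

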4.3.3 Surgery

The decision to proceed to surgery will be made by the operating surgeon using the accepted standard clinical indications. These are: 1) flail arm and Horner's syndrome 2) Toronto score less than 3.5, 3) failure to recover antigravity elbow flexion and/or antigravity shoulder abduction (AMS score for elbow flexion and/or abduction less than 5), 4) failure to bring the hand to the mouth (cookie test), or other clinical indication of lack of appropriate nerve recovery. For those infants in the study who undergo microsurgical plexus exploration, the status of each nerve root will be recorded by the operating surgeon as intact, postganglionic rupture, or pre-ganglionic avulsion. This status will be determined based on the intraoperative appearance of the nerve root as well as intraoperative SSEP testing as follows: avulsed (no repeatable response with maximal stimulation), ruptured (repeatable response to SSEPs but without distal motor function), or intact (repeatable response to SSEPs with distal motor function).

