1.1 Background

Brachial plexus birth palsy (BPBP) affects approximately 1 in 1,000 children at birth, and though the majority of infants regain full function of the affected arm, many of these injuries result in lifelong disability. Varying degrees of BPBP, from mild (neuropraxia) to severe (post-ganglionic root rupture or pre-ganglionic root avulsion), are indistinguishable on the initial clinical exam. Serial clinical examination is the current gold standard for separating infants who will recover spontaneously from those who will need reconstructive surgery. Unfortunately, this "wait and see" period may last for up to 6 months, and the effectiveness of surgery can decrease during this time. The surgeon must balance the fact that 60-80% of infants with BPBP will recover spontaneously without surgery with the knowledge that earlier nerve repair improves outcomes for infants with more severe injuries. A non-invasive diagnostic test which differentiates these two groups of infants with BPBP within weeks of birth may help improve surgeons' prognostic accuracy and therefore the treatment of this disorder. In addition, currently surgeons rely on operative exploration, visual inspection and somewhat non-specific somatosensory evoked potentials (SSEPs) to differentiate pre-ganglionic and post-ganglionic injuries, which have completely different surgical treatments. A pre-operative test that provided accurate and specific diagnosis of each root injury would improve pre-operative planning and accuracy of treatment.

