8.0 Statistical Considerations

8.1 Primary Study Endpoints

The primary endpoint is the surgeon's decision for or against surgery, typically made by 6 months of age. Surgeons will make their decision based on all available clinical data, including the MRI, but will be blinded to the neuroradiologist's scoring of the SRS and its components.

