8.4 Statistical Methods

The primary analysis for this will be assessing the discriminant ability of the SRS system to distinguish patients who do versus do not go on to surgery, by estimating the area under the receiver operating characteristic (ROC) curve with a 95% confidence interval. In addition, an optimal cutoff value for the SRS will be identified using Youden's Index which maximizes the sum of sensitivity and specificity. Sensitivity and specificity will be estimated to help quantify the utility of the SRS system to discern between surgical patient groups. The area under the ROC curve (AUC) for the SRS system may be compared to the AUC for the AMS, currently part of clinical surgical decision making, to assess whether the MRI score offers a comparable, earlier detection method for the need for surgical intervention. Secondary analysis will include comparing MRI nerve root findings at each nerve root level (C5, C6, C7, C8, and T1) with intraoperative root findings in surgical patients. Weighted kappa coefficients along with 95% confidence intervals will be estimated to assess the concordance in detecting intact, ruptured, or avulsed roots between MRI and intraoperative inspection. In addition, inter- and intra-rater reliability of the SRS will be assessed by estimating Krippendorff's alpha along with a 95% confidence interval. The AMS and Toronto evaluations at 18 and 30 months of age in the non-operative group will be used to confirm that these patients do achieve spontaneous recovery, and will be compared with the scores for the surgery group at the same time points.

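### Agreement between MRI and intraoperative root status may be inflated, because an MRI-aware surgeon records the reference and the SSEP/motor result is not analysed separately

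*Combined protocol and SAP*

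**What the plan says.** **Index reading.** Under Section 4.3.2, "the neuroradiologist will score each nerve root level as intact, post-ganglionic rupture, or pre-ganglionic avulsion".

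**Reference.** Under Section 4.3.3, "the status of each nerve root will be recorded by the operating surgeon as intact, postganglionic rupture, or pre-ganglionic avulsion". On how the surgeon reaches that call: "This status will be determined based on the intraoperative appearance of the nerve root as well as intraoperative SSEP testing". The same sentence then gives criteria based on evoked response and distal motor function: "avulsed (no repeatable response with maximal stimulation), ruptured (repeatable response to SSEPs but without distal motor function), or intact", with intact defined as a repeatable response together with distal motor function. No criteria are given for appearance, and nothing says which element governs if the two conflict.

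**What the surgeon knows.** The MRI findings go into the medical record, and Section 4.3.2 states: "Surgeons and families will be aware of these findings and will be able to view the images". The blinding is narrower. Section 8.1 says surgeons "will be blinded to the neuroradiologist's scoring of the SRS and its components", and Section 4.2.2 likewise concerns only the SRS.

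**Analysis.** Section 8.4 plans weighted kappas with confidence intervals "to assess the concordance in detecting intact, ruptured, or avulsed roots between MRI and intraoperative inspection". It does not mention SSEP when naming the reference, and it plans no sensitivity analysis for this endpoint.

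**The concern.** In an agreement study the reference should be read without knowledge of the test it is compared with. Here the person making the reference call knows the test result. Where a root is doubtful on appearance, knowledge of the MRI could pull the call toward the MRI category, and the kappa would count that as agreement. Withholding the SRS does not protect this endpoint, because Secondary Objective 1 tests the root-level MRI findings, and the report and images are open to the surgeon.

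Section 1.1 motivates the study partly by the need to tell pre-ganglionic from post-ganglionic injury before operation. This kappa is the study's evidence on that question, so readers need to know whether it was obtained against an independent reference. The confidence interval will not tell them, since it reflects sampling error only.

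**Working it through.** **No figure to reproduce.** The plan gives no expected kappa, target precision or power for root agreement. The check has two parts: what the documents establish, and what an assumed degree of influence would do.

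**1. What the documents establish**

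- Exposure: the surgeon knows the MRI report and can view the images (4.3.2).
- Room for influence: appearance is part of the call and has no criteria (4.3.3); Section 8.4 names the reference as inspection.
- Limit on influence: all three categories have SSEP/motor criteria that do not depend on MRI (4.3.3).
- Checks on the reference: none is described. The repeat and shared reads in 4.3.2 and 7.2.1 concern MRI readings and the SRS.
- Separate use of the SSEP/motor class: none is specified in 8.4.

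**2. Illustration of size**

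Weighted kappa is 1 − Do/De, where Do is the observed weighted disagreement and De the disagreement expected by chance. Suppose that, in a fraction d of the roots where surgeon and MRI would have differed, the surgeon instead records the MRI category. Do becomes (1 − d)Do and De changes little, so

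observed kappa ≈ 1 − (1 − d)(1 − kappa).

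For an assumed uninfluenced kappa of 0.60:

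| d | Calculation | Observed kappa |
|---|---|---|
| 0 | 1 − 1.0 × 0.40 | 0.60 |
| 10% | 1 − 0.9 × 0.40 | 0.64 |
| 20% | 1 − 0.8 × 0.40 | 0.68 |
| 40% | 1 − 0.6 × 0.40 | 0.76 |

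A three-category model with linear weights gives the same pattern. Its assumptions, none of them in the documents, are 30–50% of roots intact, 25–45% ruptured and 25% avulsed; MRI accuracy 70–80%; and uninfluenced surgical accuracy 85–100%. Section 8.4 does not state the weights, so linear weighting is also an assumption. With MRI accuracy 80% and surgical accuracy 90%, kappa is 0.61–0.63 at d = 0, 0.65–0.67 at 10% and 0.73–0.74 at 30%. Over all scenarios, d = 10% adds about 0.02–0.06 and d = 30% about 0.08–0.17.

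These results show what a given d implies. They are not evidence about d, because both the formula and the model impose it.

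**3. Comparison with sampling error**

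Section 8.3 aims for at least 21 surgical subjects, so 21 × 5 = 105 roots if all five levels are assessed in each. In one scenario of the model (kappa about 0.63), the simulated standard deviation is 0.148 for 21 roots at one level and 0.065 for 105 pooled roots. The 95% half-widths are 1.96 × 0.148 = 0.29 and 1.96 × 0.065 = 0.13. The pooled figure ignores clustering of roots within an infant.

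**The case against.** The strongest reply is that Section 4.3.3 already supplies an MRI-independent standard. It defines every category by SSEP response and distal motor function and lists appearance and SSEP, not MRI, as the basis of the call. If the SSEP/motor rule settles each root, the surgeon's knowledge of the MRI has no effect. Three stronger readings therefore fail:

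- A reader might infer that no MRI-independent check is planned. That is wrong, because SSEP/motor testing is one. What is missing is a specified separate analysis of it.
- A reader might infer that the kappa is inflated as a matter of fact. The documents show the opportunity for bias, not its occurrence or size.
- A reader might infer that the MRI is an input to the root call. Section 8.1 has the surgeon use the MRI in deciding whether to operate, which is a different judgement. For root status the documents show awareness only. They also do not say whether the neuroradiologist's three-category root score is itself in the medical record, although the report and images are visible either way.

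Two further points have force. The illustrative shifts of 0.04–0.08 at d = 10–20% are smaller than the sampling half-widths. And Section 4.3.1 already commits to documenting operative findings for each root; the operative form is not among the documents, so SSEP results may already be captured.

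What survives is that appearance remains part of the call, Section 8.4 describes the reference as inspection, and Section 1.1 treats SSEPs as of limited specificity, which leaves room for appearance to prevail. As the analysis is specified, only the combined call enters the kappa, so the result would not show how often that happened. Wide sampling error does not answer this, because a systematic shift lies outside what the interval measures.

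**Conclusion.** The concern holds as a possibility. The reference for Secondary Objective 1 is a combined call by a surgeon who knows the MRI findings, and the element that does not depend on MRI is not analysed on its own. Any bias would most likely raise agreement. Its size cannot be obtained from the documents: it is zero if SSEP alone decides the category, and a kappa of 0.60 would read about 0.64–0.68 if 10–20% of would-be disagreements moved to the MRI category. Both the 0.60 and the 10–20% are assumptions.

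The point affects a secondary endpoint that is estimated without a threshold or decision rule. It concerns the reference for root agreement and is separate from the primary AUC. It merits action because the remedy is cheap and uses a measurement already planned.

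**What to change.** 1. On the operative form, record for each root the SSEP/motor class already defined in Section 4.3.3, separately from the surgeon's overall call, if the form does not already do so.
2. Add to Section 8.4 a sensitivity weighted kappa, with its 95% confidence interval, of the MRI root reading against that SSEP/motor class.
3. Report the main kappa as agreement with a reference recorded with knowledge of the MRI.

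**Cost.** Up to five extra entries per operation (one per root), or about 21 × 5 = 105 entries at the planned number of surgical subjects, and one extra analysis. No procedure is added, since SSEP testing is already part of the root assessment.

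**Downside.** Because SSEP has limited specificity by the protocol's own account, a lower SSEP-only kappa could reflect SSEP misclassification as well as removal of bias, and the analysis cannot separate the two. It should remain a sensitivity analysis. If the two kappas are similar, that is some reassurance; if they differ, the report should show both and say why the difference cannot be read as the size of the bias.
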